by *Trichophyton rubrum* or *Trichophyton mentagrophytes*.

SPONSOR: DeviceFarm, Inc.
[name]
[name]

Approvals	Signature	Date
[name] CEO DeviceFarm, Inc.		

CONFIDENTIAL

SYNOPSIS

Title of Study:

A Single Center Open Label Early Feasibility Study to Evaluate the Efficacy and Safety of the RenewalNail™ Plasma Treatment System in Patients with Mild to Moderate Onychomycosis (Fungal Nail) of the Hallux caused by *Trichophyton rubrum* or *Trichophyton mentagrophytes*.

Objective:

To determine if a three-treatment protocol with the RenewalNail™ plasma treatment system over a week will result in mycological cure and/or clear nail growth on the treated hallux toe.

Methodology:

Single-center, open-label

Number of Subjects (planned):

5 Subjects

Number of Sites and Number of Subjects Per Site:

One (1) site, 5 Subjects

Diagnosis and Main Criteria for Inclusion:

Laboratory confirmed diagnosis of mild to moderate onychomycosis on at least one hallux toe caused by *Trichophyton rubrum* or *Trichophyton mentagrophytes*

Male and female Subjects of any race between 21 and 75 years of age meeting specific inclusion/exclusion criteria

Investigational Product:

RenewalNail™ Plasma Treatment System (DFPD-003)

Mode of Administration: topical

Number of treatments: 3

Duration of each treatment: 45 minutes

Criteria for Evaluation:**Efficacy:**

Mycological Cure: Two consecutive negative mycology cultures

Clinical Cure: Photographic evidence of clear nail growth

Safety:

Adverse Events

STUDY CONTACTS

SPONSOR/SITE PERSONNEL		
Name/Title	Affiliation/Address/Tel.	Responsibilities
[name] CEO	DeviceFarm Inc. [name] [name] [contact]	Sponsor Contact
[name] VP of Operations	DeviceFarm Inc. [name] [name] [contact]	Sponsor Contact
[name] Acting Head of Clinical Operations	DeviceFarm Inc. [name] [name] [contact]	Sponsor Contact/ Study Monitor
[name]	[name] [name] [contact] [contact] [name]	Principal Investigator

CONFIDENTIAL

1.0 INTRODUCTION

Background and Rationale: Onychomycosis, the most common nail disease, accounts for 30% of all cutaneous fungal infections. The disease is a progressive chronic recurring fungal infection affecting an estimated 35 million people in the United States. Approximately 50% of elderly over the age of 70 are infected as well as 30% of diabetics. Although dermatophyte infections are rarely life threatening, their high incidence and prevalence makes them an important health problem. Onychomycosis is not just a cosmetic problem, but can cause pain, difficulty walking, and susceptibility to secondary infections such as cellulitis and osteomyelitis.

Distal subungual onychomycosis (DSO) is the most common form of onychomycosis. DSO is characterized by nail discoloration, onycholysis, dystrophy of the nail plate, and accumulation of subungual debris. There is an average of 4.4 to 5.3 involved toes per patient, with an average of about 2.4 per foot. Approximately 75% of patients have both feet involved.

There are currently three groups of FDA-approved approaches to the treatment of onychomycosis: oral treatments, topical therapy, and laser treatments. Oral terbinafine (Lamisil®, Novartis Pharmaceuticals) is the lead therapy among oral medications consisting of a 250-mg tablet per day for 12 weeks for the treatment of toenail onychomycosis. Oral terbinafine yields the highest complete cure rates, between 38 and 76% depending on the clinical trial design. Oral therapy might be adequate if not for the relatively high risk of liver toxicity and drug-drug interactions. Many patients and their physicians choose not to select oral therapy due to the associated risk. Rare cases of liver failure and serious skin reactions have been reported with oral terbinafine use (Lamisil® package insert).

Topical treatment options have been researched/under development by many companies in order to provide an effective antifungal drug therapy without exposing the patient to the side effects and toxicity associated with oral antifungal drug therapy. FDA-approved topical treatments for onychomycosis include Jublia® (Valeant Pharmaceuticals), Penlac® Nail Lacquer (Dermik Laboratories) and Kerydin® (Anacor Pharmaceuticals). Topical formulations address the toxicity problem caused by the oral medications and are easy to apply. However, topical therapy has a much lower cure rate than oral therapy at 5-17% and requires significant compliance by the patient since the treatment is so long in duration (typically one year), and relatively labor intensive compared to oral therapy. Topical drug permeation can be enhanced by surgically removing the nail or disrupting the nail plate using physical techniques (manual or electrical nail abrasion, acid etching, and ablation by lasers) but the pain and inconvenience makes these unpopular choices.

Laser treatments are relatively safe, but only offer temporary cosmetic improvement (i.e., no cure). Recent publications that review the most widely used laser treatments available on the market today have concluded that they are not effective in the treatment of onychomycosis. Examples include Clearsense® laser (Sciton), Pinpointe® Footlaser (Nuvolase), Noveon® laser (Nomir Medical Technologies), GenesisPlus® laser (Cutera), and Harmony® laser (Alma Laser).

Despite improvements in outcomes with new topical antifungals and other treatment options, there is still no topical treatment that is greater than 20% effective. As a result, numerous strategies have evolved to improve efficacy and reduce reoccurrence while maintaining safety.

The Sponsor DeviceFarm, Inc. has developed the RenewalNail™ plasma treatment system to topically treat

CONFIDENTIAL

fungal infected toenails. The goal of the RenewalNail™ therapy is to overcome the shortcomings of both topical and oral therapies by combining the safety of a topical treatment with the efficacy of an oral treatment. Thus, the RenewalNail™ plasma treatment system may avoid systemic adverse events, achieve high efficacy rates, and provide a method of therapy that is not dependent on labor-intensive, long-term patient compliance as are other topical applications on the market today.

Please review the *DeviceFarm Device Description-0003* document for more details on the technology and the RenewalNail™ plasma treatment system.

2.0 STUDY OBJECTIVES

The purpose of this study is to assess the clinical feasibility of DeviceFarm, Inc.'s RenewalNail™ system and the treatment protocol that was developed based on extensive laboratory testing on human cadaver nails.

The primary objective of this study is to evaluate the efficacy and safety of the RenewalNail™ plasma treatment system and Protocol in achieving mycological cure for the patient. The Protocol calls for three 45-minute treatments performed over a week to achieve mycological cure. Mycological cure will be assessed with two consecutive mycological culture tests done over a week. Two consecutive negative mycology culture results confirm the elimination of fungus causing onychomycosis infection, as recommended by recent FDA guidance. There will be no placebo arm in the study.

Secondary objectives include:

- Will the treatment protocol result in clear nail growth for the patient over a 5-month interval?
- Is the instrument functional in a clinical setting as related to user instructions, user interface and human factor analysis?
- Are there treatment protocol or instrument changes that would improve the treatment results, patient safety, or patient comfort?
- Are there fungal species beyond *Trichophyton rubrum* and *Trichophyton mentagrophytes* that are not affected by the treatment, as seen in species identification from the nail scrapings?

3.0 INVESTIGATIONAL PLAN

3.1 Overall Study Design

DeviceFarm, Inc.'s Early Feasibility Study will be conducted as a Single-center open-label study in Subjects who meet the specified inclusion/exclusion criteria. Informed consent will be obtained. Characteristics of patients including age, gender, disease severity, and disease history will be documented during the screening visit.

Five Subjects with Distal Subungual Onychomycosis (mild to moderate DSO) infection of their big toe (hallux) nail infected by the dermatophytes *Trichophyton (T.) rubrum* or *T. mentagrophytes* will be enrolled.

Treatments will be performed at the office of the Investigator as elaborated in the **3.4 Conduct of Study** section below. The treatment protocol outlines three 45-minute treatments over the course of the first week (within 7 calendar days).

Primary study endpoint will be mycological cure, which is defined as two consecutive negative cultures following treatment. Mycological cultures will be collected (1) during screening, (2) after the third treatment, and (3) around a week (5-15 calendar days) after the third treatment.

CONFIDENTIAL

Secondary study endpoint will be clear nail growth. Photographs of the target toes will be taken throughout the study to track clear nail growth.

3.2 Discussion of Study Design

This study will be conducted as a Single-center, open-label, pilot study involving 5 Subjects. After giving informed consent, each Subject will be screened for eligibility according to inclusion/exclusion criteria. A Subject will be considered evaluable if he or she satisfies all admission criteria for entry into the study and completes the treatment protocol.

3.3 Selection of Study Population

Five adult Subjects will be prospectively enrolled in the study by the study site. There are no restrictions based on gender, race, or ethnicity. No diabetics or immunocompromised people will be enrolled. No minors under the age of 21 will be enrolled. No pregnant women will be enrolled.

3.3.1 Inclusion Criteria

- Subjects who are between 21 to 75 years (inclusive) of age;
- Subjects who are in good general health and free from any clinically significant disease that might interfere with the study evaluations;
- Subjects with established clinical diagnosis of distal subungual onychomycosis;
- Subjects with at least one big toe nail involved with 20-75% infection;
- Subjects with both positive KOH and culture for onychomycosis dermatophytes in screening of nail samples;
- Subjects whose infection is confirmed to be caused by *T. rubrum* or *T. mentagrophytes*;
- Subjects who are willing and able to refrain from employing other (non-study) treatments (traditional or alternative) for his or her toenail onychomycosis throughout study participation;
- Subjects who are willing and able to refrain from the use of nail cosmetics such as clear and/or colored nail lacquers during the week of treatment (from Study Visits 1 through 3);
- Subjects who are willing and able to give written informed consent and able to adhere to procedures and visit schedules;
- Women of childbearing potential who are currently sexually active must agree to use a medically accepted method of contraception while receiving protocol specified treatment. Methods include condoms (male or female), diaphragm or cervical cap with spermicide, medically prescribed intrauterine device, oral or systemic hormonal contraceptive, surgical sterilization (e.g., hysterectomy or tubal ligation);
- Women of childbearing potential who are not currently sexually active must agree to use a

CONFIDENTIAL

medically accepted method of contraception should they become sexually active while participating in the study;

- Women of childbearing potential must have a negative pregnancy test prior to start of study.

3.3.2 Exclusion Criteria

- Subjects with onychomycosis infection involving lunula of the affected toenail(s) or spikes of disease extending to nail matrix in the affected big toenail;
- Subjects whose foot is too large (larger than US men's size 13) or too small (smaller than US women's size 3) to properly fit into the plasma treatment device;
- Subjects whose affected big toenail cannot become normal in the opinion of the investigator;
- Subjects who received topical antifungal treatment of the nails within 2 weeks before study initiation;
- Subjects who received systemic antifungal treatment within 3 months before study initiation;
- Simultaneous participation in another clinical study or participation in another clinical study in the 30 days directly preceding treatment;
- Subjects who are immunocompromised (e.g. adrenal insufficiency, diabetes mellitus, febrile neutropenia, and the human immunodeficiency virus infected);
- Subjects with any pacemakers, or any metallic implants or prostheses in the vicinity of the treatment site (such as ankle, foot, etc.);
- Subjects with any clinically significant condition or situation, other than the condition being studied that, in the opinion of the investigator, would interfere with study evaluations or optimal participation in the study;
- Subjects who feel they cannot sit for 45 minutes at a time during the treatment;
- Subjects who are part of the staff personnel directly involved with this study or who are family members of the investigational study staff;
- Subjects with known allergy to any of the tested treatment products [i.e. perfluorocarbons and plastic polycarbonate];
- Women who are pregnant, breastfeeding, or planning pregnancy prior to the end of study participation;

3.3.3 Withdrawal Criteria

Withdrawal criteria include but are not limited to the following:

CONFIDENTIAL

- Investigator's request;
- Safety reasons (e.g., severe adverse reactions);
- Subject's request;
- Poor compliance;
- Subjects lost to follow-up. The Investigator will try to reach the Subject, twice by telephone and once by certified letter, before considering the Subject lost-to-follow-up. These actions will be reported on the Final Case Report Form and a copy of the follow-up letter will be maintained in the Investigator's file.

Treatment may be discontinued at any time by the investigator if, in his/her clinical judgment, it is in the best interest of the Subject, treatment is deemed inappropriate by a physician evaluation, or if the Subject cannot comply with the protocol. All premature discontinuations and their causes must and will be carefully documented by the Investigator on the Final Case Report Form and, if need be, on the Adverse Event Case Report Form.

Subjects who did not complete the entire study should be fully evaluated when possible. The procedures designated for the Final Visit should be completed for all Subjects discontinuing. Subjects are free to withdraw from participating in this study at any time and for whatever reason, specified or unspecified, and without prejudice.

3.3.4 Subject Identifiers

Upon screening, the Subject will be assigned a unique 3-digit Subject number that increments sequentially at the site (i.e., 001, 002). At Study Visit 1/Day 1, Subjects who are eligible for participation will retain the same Subject number for the remainder of the study. This Subject number is to be recorded on the Case Report Form for future identification and outcomes reporting.

3.4 Conduct of Study

3.4.1 Study Overview by Visit

3.4.1.1 Screening Visit

Subjects are to be screened at the Investigator's facility to determine eligibility for the study. Written informed consent is to be obtained after a careful description of the study. Written, witnessed, informed consent will be obtained from each Subject prior to participation in the study. The Subject will be given adequate time to review the informed consent document as well as address questions and concerns.

Once written informed consent is granted, Screening Visit activities will be carried out as specified in 3.4.2.1. Namely, a medical history is taken and a brief physical examination is conducted. If the Subject is confirmed to meet the inclusion/exclusion criteria besides positive mycological testing, they are assigned a Subject number and results are recorded on the Case Report Form (CRF) for each Subject. Nail scrapings are collected for fungal infection testing by KOH assay and mycological culture. Culture results will be obtained within 4 weeks of Subject's initial screening visit.

A screen failure is a Subject who received information about the study, including signing an informed consent, and possibly performing some study related procedures but was not enrolled, and did not receive study treatment. Only the Subject number, date of visit, date of consent, reason for screen failure, and study status (screen failure) will be captured in the CRF for every screen failure Subject.

3.4.1.2 Study Visit 1

The Subject will be scheduled for the first treatment as soon as positive mycological testing results are available and the Subject is confirmed to meet all inclusion/exclusion criteria. A Subject meeting all of the entry criteria is enrolled into the study. Day 1 activities will be carried out as specified in 3.4.2.2.

3.4.1.3 Study Visits 2-6

The Subject reports back to the Investigator's facility for the remainder of treatments. Investigator inquires with Subject regarding compliance, adverse events and for clinical assessment of the treated area of the foot.

Visit 2 and Visit 3 activities will be carried out as specified in 3.4.2.3 and 3.4.2.4, respectively. Mycological culture collected at Visit 3 will be the first of the two consecutive cultures for assessing mycological cure.

Visit 4 activities are specified in 3.4.2.5. Mycological culture collected at this visit will be the second of the two consecutive cultures for assessing mycological cure.

On Visit 5, mycological cultures will be collected to measure rates of reinfection/recurrence. Visit 5 activities will be carried out as specified in 3.4.2.6.

Visit 6 will be the last visit of the study and activities will be carried out as specified in 3.4.2.7.

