3.4.1.4 Discontinuation

If an eligible Subject drops out of the study for any reason, the Investigator must make every reasonable effort to obtain clinical assessments of adverse events. All data should be recorded in the CRF for the Subject and the reason for the drop out should be documented.

In the event that a Subject drops out of the study due to an adverse event, the nature of the event and its clinical course must be fully documented. The Investigator must attempt to follow the Subject until the adverse event has resolved, become clinically insignificant, stabilized, or the Subject is lost to follow-up.

Subjects who drop out of the study without completing the three 45-minute treatments over the course of the first week (within 7 calendar days) will be considered premature drop out. The Sponsor will take reasonable action to replace any of the Subjects who drop out prematurely to maintain the 5-Subject enrollment.

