3.4.2.1 Screening Visit – Baseline

- Obtain Subject's written informed consent prior to initiating any study procedures.
- Document Subject's Informed Consent in the Subject's medical record.
- Screen potential Subject according to the study inclusion/exclusion criteria.
- Take the Subject's medical history.
- Perform a brief physical exam.
- Perform urine pregnancy test on women of childbearing potential.
- Photograph the infected hallux nail(s).
 - If both hallux nails are infected and meet the inclusion/exclusion criteria, both nails can be photographed and tested for KOH and mycology. If both are positive for KOH and culture, the Investigator will choose one and only treat that one in the study.
- Perform KOH testing of infected hallux nail(s): Before obtaining a specimen, make sure the nail is clipped and cleansed with an alcohol swab to remove bacteria and debris.
- Collect mycology sample for lab culture: Prepare and ship the mycology samples according to the instructions from the designated mycology laboratory.

3.4.2.2 Study Visit 1 - Day 1

- Check for conformance to inclusion/exclusion criteria.
- Perform debridement on the infected nail to be treated.
- Notch the nail.
- Measure distance between proximal nail fold and notch.
- Insert the Disposable into the RenewalNail™ plasma treatment device.
- Brush the top, edges, and underside of the infected nail with the Nail Penetration Enhancer.
- Insert the Subject's foot into the opening of the Disposable that was placed the device.
- Ensure that the Subject's foot is properly inserted into the device with a seal of the Disposable flexible material around the foot.
- Push the device power button to start the treatment.
- Complete the 45-minute plasma treatment.
- Perform clinical evaluation of the toes after plasma treatment as specified in “5.0 Safety Assessment/Risks”
- Check on occurrence of adverse events. Stop protocol if any serious adverse events occur.
- Photograph the treated nail.

3.4.2.3 Study Visit 2

Study Visit 2 should occur no sooner than 36 hours after Study Visit 1. In no circumstance should the Subject receive treatment on two (2) consecutive days.

- Check on occurrence of adverse events.
- Perform a plasma treatment per instructions in the *Instructions for Use of the DeviceFarm RenewalNail Plasma Generator DFPD-003* document.
- Perform clinical evaluation of the toes after plasma treatment as specified in “5.0 Safety Assessment/Risks”
- Photograph the treated nail.

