3.4.2.4 Study Visit 3

Study Visit 3 should occur no sooner than 36 hours after Study Visit 2, but within 7 calendar days from Study Visit 1. In no circumstance should the subject receive treatment on two (2) consecutive days

- Check on occurrence of adverse events.
- Perform a plasma treatment per instructions in the *Instructions for Use of the DeviceFarm RenewalNail Plasma Generator DFPD-003* document.
- Perform clinical evaluation of the toes after plasma treatment as specified in “5.0 Safety Assessment/Risks”
- Perform fungal scrapings for mycological culture as instructed by the laboratory.
- Photograph the treated nail.

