4.0 EFFICACY ASSESSMENT

4.1 Photographic Documentation

Baseline photographs will be taken of the infected nails at the Screening Visit prior to KOH and mycology sampling since these sampling procedures require much of the infected nail to be removed in order to reach the site of active infection.

Photographs will be taken of the treated nail at the end of each Study Visit to document the appearance

CONFIDENTIAL

of the nail following each visits' procedures and to allow for photographic assessment of clear nail growth over the course of the study.

All photographs should be done with the digital camera provided by the Sponsor and following the instructions provided in the *Instructions for Use of the DeviceFarm Nail Photography* document.

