9.0 Statistical Methods Planned

Due to the nature of the study and the small number of Subjects, no inferential statistical analyses will be performed. The results from this study will be used to determine whether the treatment can achieve mycological cure for onychomycosis Subjects fulfilling the inclusion/exclusion criteria.

Mycological cure is defined as an achievement of negative culture results for both *Trichophyton rubrum* and *Trichophyton mentagrophytes* from both Visit 3 and Visit 4.

The data is too small to summarize with descriptive statistics; therefore, Subject listings will be presented.

CONFIDENTIAL

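### Mycological cure rests on cultures about 0 and 2–10 days after the last treatment, the Day 42 culture cannot qualify it, and the second culture has two conflicting windows

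*Protocol*

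**What the plan says.** Section 3.4.1.3 assigns the cultures: "Mycological culture collected at Visit 3 will be the first of the two consecutive cultures for assessing mycological cure". The Visit 4 culture is the second of the pair. Section 9.0 repeats this in the analysis definition, which requires negative results for both named species "from both Visit 3 and Visit 4".

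Section 3.4.2.4 lists the Visit 3 scraping after the plasma treatment given at that visit. Section 3.4.2.5 sets Visit 4 at Day 12 ± 3 days, whereas section 3.1 places the same culture 5 to 15 calendar days after the third treatment.

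On what the pair means, section 2.0 says: "Two consecutive negative mycology culture results confirm the elimination of fungus causing onychomycosis infection". The sentence goes on to attribute this to recent FDA guidance. The same section says: "There will be no placebo arm in the study".

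A further culture is taken at Visit 5 (Day 42 ± 3, section 3.4.2.6). Section 3.4.1.3 gives it the role of measuring reinfection or recurrence. It is missing from the list of cultures in section 3.1 and from the definition in section 9.0. Visit 6 (section 3.4.2.7) has no culture.

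**The concern.** The primary endpoint is read immediately after treatment and again within days, yet section 2.0 treats two negatives as proof that the fungus has gone. The protocol gives no figures on residual treatment effect or on how often culture misses live infection.

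Its own procedures suggest another possible reason for an early negative. Section 4.1 says of the screening samples that "these sampling procedures require much of the infected nail to be removed in order to reach the site of active infection", and the Visit 1 steps in section 3.4.2.2 include "Perform debridement on the infected nail to be treated". The positive entry culture precedes that debridement and both cure cultures follow it.

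The one culture taken weeks later could show whether negativity lasted, but no stated rule connects it to cure status. Section 9.0 says the results will be used to determine whether the treatment can achieve mycological cure. With five subjects, each label carries weight in that judgement.

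The two windows raise a separate problem: a single Visit 4 culture can comply with one section and deviate from another.

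**Working it through.** **Visit 3 day.** Take Visit 1 as Day 1. Sections 3.4.2.3 and 3.4.2.4 require at least 36 hours between treatments and bar consecutive days, so Visit 2 is Day 3 at the earliest and Visit 3 is Day 5 at the earliest. For the upper limit, sections 3.1 and 3.4.1.4 place all three treatments in the first week, glossed as seven calendar days, which gives Day 7. Section 3.4.2.4 is looser: "Study Visit 3 should occur no sooner than 36 hours after Study Visit 2, but within 7 calendar days from Study Visit 1". Counted as Visit 1 plus 7 days, that gives Day 8. Day 5–7 is the main reading below and Day 8 is the alternative.

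**Time from last treatment to each culture.**
- Visit 3: about 0 days, because it follows the treatment at the same visit.
- Visit 4 (Day 12 ± 3 = Day 9–15): minimum 9 − 7 = 2 days, maximum 15 − 5 = 10 days. With Day 8 the minimum is 9 − 8 = 1 day.
- Visit 5 (Day 42 ± 3 = Day 39–45): minimum 39 − 7 = 32 days, maximum 45 − 5 = 40 days. With Day 8 the minimum is 39 − 8 = 31 days.

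**Can the 5–15 days in section 3.1 be reproduced from the visit schedule?** No. The schedule yields 2–10 days. Gap = Visit 4 day − Visit 3 day, and a pair complies with section 3.1 if the gap is 5 to 15.

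| Visit 3 | Gaps under section 3.4.2.5 | Pairs meeting section 3.1 | Visit 4 days in breach | Days allowed by section 3.1 | Of these, outside Day 9–15 |
|---|---|---|---|---|---|
| Day 5 | 4–10 | 6 of 7 | 9 | 10–20 | 5 of 11 |
| Day 6 | 3–9 | 5 of 7 | 9–10 | 11–21 | 6 of 11 |
| Day 7 | 2–8 | 4 of 7 | 9–11 | 12–22 | 7 of 11 |
| Day 8 (alternative) | 1–7 | 3 of 7 | 9–12 | 13–23 | 8 of 11 |

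- Day 5–7: 6 + 5 + 4 = 15 of 21 pairs comply, so 6 breach section 3.1. In the other direction, 5 + 6 + 7 = 18 of 33 dates allowed by section 3.1 fall outside section 3.4.2.5.
- Day 5–8: 15 + 3 = 18 of 28 pairs comply, so 10 breach.
- The longest gap the schedule allows is 10 days, so the 11–15 days that section 3.1 permits cannot be reached.
- At the nominal Day 12 the gaps are 7, 6 and 5 days for Visit 3 on Day 5, 6 and 7, and all comply. After a Day 8 Visit 3 the gap is 12 − 8 = 4 days, which does not.

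These are counts of allowed calendar days, not probabilities.

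**Cure status by culture sequence (Visits 3/4/5).** Under section 9.0, negative/negative/negative is a cure. Negative/negative/positive is also a cure, because the third result does not enter the definition. The two subjects receive the same primary label.

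**The case against.** The strongest reply is that this is an openly uncontrolled early feasibility study of five subjects, with listings and no inference. A missing control arm is not an error in such a study. The objective concerns the system together with its protocol, and debridement is part of that protocol, so separating device from debridement is not a stated aim. The two-negative criterion is attributed to FDA guidance, and nothing here shows that it departs from that source. Section 4.2 asks for specimens close to the cuticle, which bears on how far debridement could explain a negative. The Visit 5 culture is collected, recurrence may include return of the original infection, and listings for five subjects would let a reader see a negative/negative/positive sequence. Clear nail growth is followed to Day 168. Further tabulation of Visit 5 may sit in an analysis plan that is not shown.

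Most of this stands, and it limits the point. It does not rescue the wording in section 2.0, which claims confirmation from two cultures within days of treatment. Nor does it supply a link between Visit 5 and cure, because the protocol itself fixes both the definition and the role of Visit 5.

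A reader might infer three stronger things that the documents do not support:
- **That the early negatives are false, or that cure is overstated by a known amount.** The protocol gives no culture sensitivity and no data on residual effect.
- **That the endpoint must be renamed throughout or a control arm added.** Renaming would not separate nail removal from treatment effect, and the Visit 3/Visit 4 definition is a legitimate early endpoint if it is described as such.
- **That the window conflict changes who is cured.** Section 9.0 classifies by visit, not by day. Day 12–15 satisfies both sections for every Visit 3 on Day 5–7.

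**Conclusion.** The point holds in a limited form and should be fixed. The primary result shows culture negativity at about 0 and 2–10 days after the last treatment (1–10 days if Day 8 is allowed). In this design that is not confirmed elimination. Whether the cited guidance supports the stronger wording cannot be judged from the protocol. A subject positive at Visit 5, some 32–40 days after treatment (31–40 with Day 8), keeps the label of cure. How often that would happen is unknown.

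The window conflict is certain but partial: 6 of 21 permitted day pairs breach section 3.1, or 10 of 28 if Visit 3 may fall on Day 8. Under the Day 5–7 reading it lies at the edges of the Visit 4 window. Under the Day 8 reading it can reach the nominal day. It is a matter of protocol compliance only. The counts assume Day 1 is Visit 1 and whole calendar days.

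**What to change.** 1. Keep the Visit 3/Visit 4 endpoint, but reword section 2.0 so that it does not say these early negatives confirm elimination.
2. List the Visit 3, 4 and 5 culture results in sequence for each subject. Beside the primary result, report sustained negativity (all three negative). Describe a subject negative at Visits 3 and 4 and positive at Visit 5 as *not sustained: persistence or reinfection cannot be distinguished*. Add the Visit 5 culture to the list in section 3.1.
3. Reconcile sections 3.1 and 3.4.2.5 so that the second culture has one window, and state whether Visit 3 may fall on Day 8.

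This needs no extra visit, culture or subject, only the written sponsor and IRB approval required by section 9.2. The headline becomes less favourable, and the sustained result is available only after Visit 5. A true reinfection by Day 42 would be listed as not sustained. That is possible, since only one hallux is treated (section 3.4.2.1) and section 1.0 gives an average of 4.4 to 5.3 involved toes per patient. The early result would be unaffected.
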